Record SAEs related to study participation, or to a concurrent GSK medication/vaccine		●	●	●	●		●	●	●			●	●			●	●		●					
Record SAEs (All, fatal, related to the investigational vaccine) ^p		●	●	●	●		●	●	●			●	●			●	●		●					
Record AEs of specific interest ^l		●	●	●			●	●	●			●	●			●	●		●					
Study Conclusion																								

CONFIDENTIAL

204889 (MALARIA-094)
Protocol Amendment 3 Final

Epoch	Epoch 001												Epoch 002				Epoch 003				Epoch 004			
	Visit 1 ^m Screening	Visit 2	Visit 3	Visit 4	Visit 5 ^a	Visit 6 ^a	Visit 10 ^b	Visit 11 ^b	Visit 12 ^b	Visit 18 ^c	Visit 19 ^c	Visit 24 ^d	Visit 25 ^e	Visit 27 ^c	Visit 28 ^c	Visit 30 ^f	Visit 31 ^f	Visit 33 ^c	Visit 34 ^c	Visit 38				
Type of contact: Clinic visits	D-28 to D-1	D0	M1	M2	M2 + 7d	M3	M7	M7 + 7d	M8	M14	M15	M20	M21	M26	M27	M32	M33	M38	M39	M50				
Timepoints																								
Children age (Months)		5-17 m																						
For the reactogenicity sub-cohort only:										●	●	●												
Blood sampling for assessment of safety (1.0 ml)																								
Record solicited local and general AEs (Days 0-3)								● ^j						● ^j				● ^j						

Note: The double-line border following Month 21 (Visit 25) and Month 33 (Visit 31) indicates the two interim analyses which will be performed on all data collected up to respectively Month 21 and up to Month 33 (i.e. data that are as clean as possible, except clinical malaria fully cleaned up to Month 14). The final analysis will be performed on fully cleaned data collected up to study end (Month 50).

D: Day, M: Month.

● is used to indicate a study procedure that requires documentation in the individual eCRF.

O is used to indicate a study procedure that does not require documentation in the individual eCRF.

- a. Clinic visit 5 (Month 2 + 7 days) and clinic visit 6 (Month 3) are only for groups R012-20, R012-14-mD, Fx012-14-mFxD and Control. The group Fx017-mFxD has a field worker visit at Month 3 for assessment of parasitemia.
- b. Clinic visit 10 (Month 7), clinic visit 11 (Month 7 + 7 days) and clinic visit 12 (Month 8) are only for group Fx017-mFxD. The other groups have field worker visits at Month 7 and Month 8 respectively for assessment of parasitemia.

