- c. Clinic visit 18 (Month 14), clinic visit 19 (Month 15), clinic visit 27 (Month 26), clinic visit 28 (Month 27), clinic visit 33 (Month 38) and clinic visit 34 (Month 39) are only for groups R012-14-mD and Fx012-14-mFxD. The other groups have field worker visits at Month 14, Month 15, Month 26 and Month 38 respectively for assessment of parasitemia.
- d. Clinic visit 24 (Month 20) is only for groups R012-20, Fx017-mFxD and Control. The other groups have a field worker visit at Month 20 for assessment of parasitemia.
- e. Clinic visit 25 (Month 21) is only for groups R012-20 and Fx017-mFxD.
- f. Clinic visit 30 (Month 32) and clinic visit 31 (Month 33) are only for group Fx017-mFxD. The other groups have a field worker visit at Month 32 for assessment of parasitemia.
- g. The screening laboratory results (hemoglobin) must be checked during the screening activities and before randomization.
- h. There is no specific section in the eCRF to record the contraindications, warnings and precautions. The absolute contraindications to further administration of study vaccines have to be recorded in the AE or SAE section of the eCRF.
- i. At screening, hemoglobin will be assessed in all subjects screened.
- j. Solicited local and general AEs will be collected in the first 50 subjects enrolled in each group (reactogenicity sub-cohort) during four days (day of vaccination and three subsequent days) after vaccination as indicated in the table above. On the day of vaccination the evaluation will be carried out by the study physician at the study center. On Days 1, 2 and 3 after vaccination, trained study personnel will visit the children to record solicited AEs on diary cards.
- k. Unsolicited AEs will be collected during 30 days (day of vaccination and 29 subsequent days) after each dose of study vaccine. Unsolicited AEs will be captured through passive surveillance at inpatient and outpatient facilities and during study visits.

CONFIDENTIAL

204889 (MALARIA-094)
Protocol Amendment 3 Final

- I. AEs of specific interest include all seizures occurring within 30 days post-vaccination, meningitis and pIMDs (see Section 9.1.6). pIMDs will be reported via the electronic Expedited Adverse Events Report. Meningitis and seizures will be reported via the electronic Expedited Adverse Events Report and in addition clinical details of each case will be reported in a specific eCRF screen.

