- m. If a subject is considered momentarily ineligible on the day of the screening visit (i.e. failing to meet one or more eligibility criteria) procedures for screening can be repeated one further time, within the time window allowed for screening (see [Table 14](#)). No more than one repeat is allowed.
- n. Blood for parasitemia (0.5 ml) includes the blood for the slide reading (**to Month 50**) and for the filter paper (**to Month 32**). The parasitemia assessment by blood slide reading will include blood-stage parasites and gametocytes counts.
- o. In addition to the scheduled clinic visits, malaria cases will be captured by PCD throughout the study. All sick children presenting with fever and/or history of fever will have a blood sample taken for the evaluation of vaccine efficacy (for blood slide **to Month 50** and filter paper for PCR **to Month 32**).
- p. Case of severe malaria or cerebral malaria will be reported via the electronic Expedited Adverse Events Report (refer to Section 9.3.1) and in addition clinical details of each case will be reported in a specific eCRF screen.

Amended 14 November 2019

Table 12 List of study procedures for field worker visits - Part 1 (Day 0 to Month 19)

Epochs	Epoch 001																			Epoch 002										
	Visit a*	Visit b*	Visit c*	Visit 6	Visit 7	Visit 8	Visit 9	Visit 10	Visit d*	Visit e*	Visit f*	Visit 12	Visit 13	Visit 14	Visit 15	Visit 16	Visit 17	Visit 18	Visit g*	Visit h*	Visit i*	Visit 19	Visit 20	Visit 21	Visit 22	Visit 23				
Type of contact: Field worker visits	M2 + 1d	M2 + 2d	M2 + 3d	M3	M4	M5	M6	M7	M7 + 1d	M7 + 2d	M7 + 3d	M8	M9	M10	M11	M12	M13	M14	M14 + 1d	M14 + 2d	M14 + 3d	M15	M16	M17	M18	M19				
Timepoints																														
Control group																														
Check subject's identification card	0	0	0		0	0	0	0				0	0	0	0	0	0	0				0	0	0	0	0	0	0		
Blood sampling for assessment of parasitemia for ALL subjects (0.5 ml) †,§					•	•	•	•				•	•	•	•	•	•				•	•	•	•	•	•	•	•		
For the reactogenicity sub-cohort only: Record solicited local and general AEs (Days 0-3)	•	•	•																											
Group R012-20																														
Check subject's identification card	0	0	0		0	0	0	0				0	0	0	0	0	0	0				0	0	0	0	0	0	0		
Blood sampling for assessment of parasitemia for ALL subjects (0.5 ml) †,§					•	•	•	•				•	•	•	•	•	•				•	•	•	•	•	•	•	•		
For the reactogenicity sub-cohort only: Record solicited local and general AEs (Days 0-3)	•	•	•																											

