9.1.5. Severe malaria and cerebral malaria

All cases of severe malaria and cerebral malaria will be reported as SAEs as part of the safety surveillance until study end (Month 50) and clinical details of each case will be reported in a specific eCRF screen. Case definitions adapted from the WHO case definitions of severe malaria and cerebral malaria will be used as reference for diagnosis. Refer to [APPENDIX C](#) for the case definitions.

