9.2.3. Evaluation of adverse events and serious adverse events

9.2.3.1. Active questioning to detect adverse events and serious adverse events

As a consistent method of collecting AEs, the subject's parent(s)/LAR(s) should be asked a non-leading question such as:

'Has your child acted differently or felt different in any way since receiving the vaccines or since the last visit?'

When an AE/SAE occurs, it is the responsibility of the investigator to review all documentation (e.g. hospital progress notes, laboratory and diagnostics reports) relative to the event. The investigator will then record all relevant information regarding an AE/SAE in the eCRF. The investigator is not allowed to send photocopies of the subject's medical records to GSK Biologicals instead of appropriately completing the eCRF. However, there may be instances when copies of medical records for certain cases are requested by GSK Biologicals. In this instance, all subject identifiers will be blinded on the copies of the medical records prior to submission to GSK Biologicals.

The investigator will attempt to establish a diagnosis pertaining to the event based on signs, symptoms, and/or other clinical information. In such cases, the diagnosis should be documented as the AE/SAE and not the individual signs/symptoms.

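### Recording of SAEs, AESIs and AEs leading to withdrawal from vaccination is scheduled only at clinic visits, so the visit-prompted part of safety ascertainment differs by arm (2 to 8 clinic visits after Month 3)

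*Protocol*

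**What the plan says.** Arm names follow the SAP: R012-14, Fx012-14 and Fx017-20 are the protocol's R012-14-mD, Fx012-14-mFxD and Fx017-mFxD.

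Table 11 in Protocol Section 6.5 lists procedures at clinic visits. For every group it has rows for SAEs, for AEs/SAEs leading to withdrawal from vaccination, and for AESIs ("Record AEs of specific interest"). Tables 12 and 13 list procedures at field worker visits: the identification-card check, the parasitemia blood sample and, in the reactogenicity sub-cohort, solicited AEs. They have no row for SAEs, AESIs or AEs leading to withdrawal.

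The footnotes to Table 11 assign clinic visits by dosing schedule:
- Footnote b: "Clinic visit 10 (Month 7), clinic visit 11 (Month 7 + 7 days) and clinic visit 12 (Month 8) are only for group Fx017-mFxD".
- Footnote c: "clinic visit 33 (Month 38) and clinic visit 34 (Month 39) are only for groups R012-14-mD and Fx012-14-mFxD", and likewise for Months 14, 15, 26 and 27. It continues: "The other groups have field worker visits at Month 14, Month 15, Month 26 and Month 38 respectively for assessment of parasitemia".
- Footnote d: "Clinic visit 24 (Month 20) is only for groups R012-20, Fx017-mFxD and Control".
- Footnotes e and f give Month 21 to R012-20 and Fx017-20, and Months 32 and 33 to Fx017-20 alone.

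Section 9.2.3.1 sets out one non-leading question to parents, introduced with "As a consistent method of collecting AEs". It does not say at which type of visit the question is asked. Section 9.2.1 has SAEs and AESIs collected in every group from first vaccination to Month 50.

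**The concern.** The trial is open-label. Protocol Section 11.10 and SAP Section 7.5.1 tabulate cumulative percentages of subjects with SAEs, severe malaria, meningitis and pIMDs by group, to several cut-offs up to Month 50. Meningitis and delayed severe malaria are named risks in Protocol Table 1, and both are described there by comparison with a control group. For such a comparison each arm should be asked about events in the same way and about equally often.

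The schedule does not provide that. At the Month 33 analysis, the last clinic visit with SAE and AESI rows was Month 20 in Control and Month 21 in R012-20. It was Month 27 in R012-14 and Fx012-14, and Month 33 in Fx017-20. The contrast between yearly full doses and the standard schedule (R012-14 against R012-20), which bears on the regulator's question about multiple yearly doses, has 7 against 3 such visits after Month 3. Meanwhile field workers see children in every arm many times with no scheduled safety question.

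What is at stake is a possible difference between arms in how completely late serious events are picked up, which could be removed at contacts that already take place.

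**Working it through.** The documents state no count of clinic visits per arm, so there is no figure to reproduce. The check is a count.

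**Inputs.** Clinic visits come from the Table 11 columns, assigned to arms by footnotes a to f. Parasitemia contacts come from Figure 2 and Table 20. Dose times come from Table 23.

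**Clinic visits after Month 3**
- Control: M20, M50.
- R012-20: M20, M21, M50.
- R012-14 and Fx012-14: M14, M15, M26, M27, M38, M39, M50.
- Fx017-20: M7, M7+7d, M8, M20, M21, M32, M33, M50.

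**Clinic visits before that.** Four arms have Day 0, M1, M2, M2+7d and M3 (5 visits). Fx017-20 has Day 0, M1 and M2 (3 visits).

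| Arm | Clinic, after M3 | Clinic, Day 0 to M50 | Clinic, after own Dose 3 visit | Longest gap, months | Field visits, after M3 |
|---|---|---|---|---|---|
| Control | 2 | 5+2 = 7 | 4 | 50−20 = 30 | 25 |
| R012-20 | 3 | 5+3 = 8 | 5 | 50−21 = 29 | 25 |
| R012-14 | 7 | 5+7 = 12 | 9 | 50−39 = 11 | 22 |
| Fx012-14 | 7 | 5+7 = 12 | 9 | 50−39 = 11 | 22 |
| Fx017-20 | 8 | 3+8 = 11 | 7 | 50−33 = 17 | 22 |

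Control and R012-20 also each have an earlier gap of 20−3 = 17 months.

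**Contacts common to all arms.** Parasitemia contacts after Month 3 are monthly from M4 to M20 (17) and three-monthly from M23 to M50 (10), so 27 in every arm. Control and R012-20 make two of these in clinic (M20, M50), leaving 27−2 = 25 for field workers. R012-14 and Fx012-14 make five in clinic (M14, M15, M26, M38, M50), and so does Fx017-20 (M7, M8, M20, M32, M50), leaving 27−5 = 22.

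**Dependence on the cut-off.** Counting from Month 3 includes Fx017-20's Dose 3 visits (M7 to M8) and leaves out the matching visits of the other arms (M2 to M3). Over the whole study, or after each arm's own Dose 3 visit, the maximum is in R012-14 and Fx012-14. Control is lowest on all three counts and has the longest gap.

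**Which events are affected.** Unsolicited AEs are collected for 30 days after each dose, and every dose in every arm is followed by a clinic visit about a month later, so scheduled capture per dose is balanced. Solicited AEs are recorded by field workers in the sub-cohort. That leaves SAEs, AESIs and AEs/SAEs leading to withdrawal. Seizures count as AESIs only within 30 days of a dose, so among AESIs the point bears mainly on meningitis and pIMDs.

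**The case against.** The strongest reply is that a row in a procedures table is not the ascertainment system. Section 9.2.1 makes SAE and AESI collection continuous for all groups. Table 30 ties reporting to awareness, within 24 hours, and not to a visit. Parents are told to contact the investigator about anything they perceive as serious and to bring an unwell child to the health center. Verbal autopsy covers deaths outside hospital where an autopsy cannot be done. All of this is the same in every arm, and it stands: only the increment prompted by a visit can differ.

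Second, Section 9.2.3.1 does not confine its question to clinic visits, Table 14 lists field worker visits among the study visits, and the study procedures manual, which is not available here, may assign the question to field workers. This stands in part. The question may be asked in practice, but Section 3 makes adherence to Section 6.5 a requirement, and the field worker tables there leave SAE and AESI recording out. A silence in 9.2.3.1 does not fill that omission.

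Third, the endpoints limit what a late question can add. Severe malaria needs a positive slide or rapid test plus clinical or laboratory criteria, and confirmed meningitis needs cerebrospinal fluid. A parent's recall cannot supply these. This also stands and is a reason to expect a modest effect.

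Fourth, the direction of any bias is not settled. R012-20 is scheduled almost like Control despite its fourth dose, and Fx017-20 has a 17-month gap of its own at the end. Section 11.7.1 adds that differing exposure may influence health-seeking, so facility-based capture could itself differ between Control and vaccine arms.

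**Conclusion.** The point holds for SAEs, AESIs and AEs/SAEs leading to withdrawal from vaccination. Their scheduled recording is confined to clinic visits numbering 2, 3, 7, 7 and 8 after Month 3 (Control, R012-20, R012-14, Fx012-14, Fx017-20), or 7, 8, 12, 12 and 11 from Day 0, with longest gaps of 30, 29, 11, 11 and 17 months. It rests on reading Tables 12 and 13 as the full list of field worker duties and on children following the schedule. It is a worthwhile, inexpensive improvement; it does not show that the safety data are invalid.

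A reader might infer more, and the documents do not support it:
- That safety incidence is biased upward in the multi-dose arms, by some ratio, or that a false signal will arise. No document gives the share of events caught by facility surveillance or recovered by questioning, so any ratio would rest on invented inputs. Safety is tabulated as percentages with exact confidence intervals, with no planned between-group test.
- That all AE recording is unequal. Solicited AEs and 30-day unsolicited AEs are not affected.
- That Fx017-20 is the most closely questioned arm. That ranking depends on the Month 3 cut-off.
- That field workers see every child on one schedule. The 27 contact months are common, but field workers make 25 of them in two arms and 22 in three.

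**What to change.** Add to Tables 12 and 13, for every group at every scheduled parasitemia field visit, an eCRF-documented row: ask the Section 9.2.3.1 question and refer any hospitalization, death, seizure or suspected meningitis since the last visit to the investigator for SAE/AESI recording. State in Section 9.2.1 that field worker visits are scheduled contacts for SAE and AESI detection in all groups. If field workers already ask the question under the study procedures manual, the change only puts that in the protocol.

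Cost: no new visit, sample or assessor. Field visits after Month 3 sum to 25+25+22+22+22 = 116 across the arms. With 300 children per arm that is up to 116 × 300 = 34,800 short entries; Fx017-20's Month 3 field visit adds 300. There would also be a few minutes per visit and some additional SAE reports to process.

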6.6. Detailed description of study procedures

6.6.1. Informed consent

The signed/witnessed/thumb-printed informed consent of the subject's parent(s)/LAR(s) must be obtained before study participation. Refer to Section 6.1 for the requirements on how to obtain informed consent.

6.6.2. Check inclusion and exclusion criteria

Check all inclusion and exclusion criteria as described in Sections 5.2 and 5.3 before enrolment.

If a subject is considered momentarily ineligible on the day of the screening visit (i.e. failing to meet one or more eligibility criteria) procedures for screening can be repeated one further time, within the time window allowed for screening (see Table 14). No more than one repeat is allowed.

6.6.3. Check the subject's vaccination card

Check the subjects' vaccination card to assess if the subject meets the related inclusion criterion described in Section 5.2.

6.6.4. Check screening laboratory results

Check the result of the hemoglobin level to assess if the subject meets the related exclusion criterion described in Section 5.3.

6.6.5. Collect demographic data

Record demographic data such as date of birth and gender in the subject's eCRF.

6.6.6. Check medical history

Obtain the subject's medical history by interview and/or review of the subject's medical records and record any pre-existing conditions or signs and/or symptoms present in a subject prior to the first study vaccination in the eCRF.

6.6.7. Physical examination

Perform a physical examination of the subject, including assessment of body temperature, heart rate and respiratory rate. Collected information needs to be recorded in the eCRF at Visit 1 (Screening).

Physical examination at each study visit subsequent to the first visit will be performed only if the subject indicates during questioning that there might be some underlying pathology(ies) or if deemed necessary by the investigator or delegate.

Treatment of any abnormality observed during physical examination has to be performed according to local medical practice outside this study or by referral to an appropriate health care provider.

6.6.8. Measure and record length and weight

Perform anthropometric measurements of the subject (length and weight) at Visit 1 (Screening). Collected information needs to be recorded in the eCRF.

The methodologies used for length and weight measurements have been adapted from Cogill [Cogill, 2003] and are based on guidelines of the United Nations [United Nations, 1986]. These procedures are fully described in the SPM.

6.6.9. Issue subject's identification card

At Visit 2, take a picture of the subject and his/her parent(s)/LAR(s) to make an identification card with subject's picture and number. Give this identification card to the subject's parent(s)/LAR(s).

6.6.10. Check subject's identification card

At each subsequent clinic visits AND field worker visits, check the subject's identification card.

6.6.11. Study group and treatment number allocation (randomization)

Study group and treatment number allocation will be performed as described in Section 6.2.2. The number of each administered treatment must be recorded in the eCRF.

6.6.12. Record if the subject belongs to the reactogenicity sub-cohort

The reactogenicity sub-cohort will consist of the first 50 subjects enrolled in each group (see Section 5). Record in the eCRF if the subject belongs to the reactogenicity sub-cohort.

6.6.13. Check contraindications, warnings and precautions to vaccination

Contraindications, warnings and precautions to vaccination must be checked at the beginning of each vaccination visit. Refer to Sections 7.5 and 7.6 for more details.

6.6.14. Record pre-vaccination body temperature

The axillary, rectal, oral or tympanic body temperature of all subjects needs to be measured prior to any study vaccines administration. The preferred route for recording temperature in this study will be axillary. If the subject has fever (fever is defined as temperature $\geq 37.5^{\circ}\text{C}/99.5^{\circ}\text{F}$ for oral, axillary or tympanic route, or $\geq 38.0^{\circ}\text{C}/100.4^{\circ}\text{F}$ for

rectal route) on the day of vaccination, the vaccination visit will be rescheduled within the allowed interval for this visit (see [Table 14](#)).

6.6.15. Study vaccines administration

After completing all prerequisite procedures prior to vaccination, one dose of study vaccine will be administered intramuscularly in the left deltoid (refer to Section [7.3](#) for detailed description of the vaccines administration procedure). If the investigator or delegate determines that the subject's health on the day of administration temporarily precludes vaccine administration, the visit will be rescheduled within the allowed interval for this visit (refer to [Table 14](#)).

The subjects will be observed closely for at least 30 minutes following the administration of the vaccine, with appropriate medical treatment readily available in case of anaphylaxis.

Vaccination will take place at the vaccination center. All vaccinations will be given by a qualified person: a nurse or a doctor. A staff member experienced in the resuscitation of children will be available at all vaccination sessions.

6.6.16. Blood sampling for all subjects

Blood samples will be taken during certain study visits as specified in [Table 11](#), [Table 12](#) and [Table 13](#).

Refer to the Module on Biospecimen Management in the SPM for detailed instructions for the collection, handling and processing of the samples.

- **Blood sampling for assessment of immunogenicity**

A volume of approximately 2.5 ml of whole blood should be drawn from all subjects at each pre-defined timepoint. Out of this, a volume of approximately 1.5 ml of whole blood will provide 600 µl of serum (300 µl of serum for anti-CS enzyme-linked immunosorbent assay [ELISA] + anti-CS avidity and 250 µl of serum for anti-HBs) and serum from a volume of approximately 1.0 ml of whole blood will be stored to support potential ancillary studies for the further characterization of the immune response and translational research for correlates of protection.

After centrifugation, serum samples should be kept at -20°C/ -4°F or below until shipment. Refer to the SPM for more details on sample storage conditions.

- **Blood sampling for assessment of hemoglobin at screening**

A volume of approximately 0.5 ml of whole blood should be drawn from all subjects screened at Visit 1 (Screening) to measure hemoglobin concentration.

- **Blood sampling for assessment of parasitemia**

A volume of approximately 0.5 ml of whole blood should be drawn from all subjects at each pre-defined timepoint for the assessment of *P. falciparum* parasitemia (**until Month 50** for blood slide and **until Month 32** for filter paper).

In addition to the scheduled clinic visits, malaria cases will be captured by PCD throughout the study. All sick children presenting with fever and/or history of fever will have a blood sample taken for the evaluation of vaccine efficacy (***until Month 50*** for blood slide and ***until Month 32 for*** filter paper).

Amended 14 November 2019

